#### **Statistical Procedures:**

The primary endpoint for this pilot trial will be a serious adverse event rate greater than 30%, which is an acceptable rate, based on prior clinical trial data with sodium-glucose cotransporter 2 inhibitors in subjects with heart failure over a 3 month period. Secondary endpoints will include mean change in daily diuretic dose (mg/kg of furosemide equivalence), mean change in body weight (kg) and total water content (kg), and mean change in Kansas City Cardiomyopathy Questionnaire (KCCQ) score and Short Physical Performance Battery (SPPB) score. In preliminary analyses, we will describe the baseline characteristics of subjects. In particular, we will present summary measures on patient age, sex, diabetes status, renal function, NT-proBNP level, KCCQ score, SPPB score, daily diuretic dose, echocardiographic features, and body composition analysis (including body weight and total water content). Continuous variable distributions will be assessed for normality and skewness, and log transform applied when appropriate. A matched-paired t-test will be used to test for a significant difference in the means of measured secondary endpoints pre- and post-treatment with empagliflozin 10 mg oral daily for 3 months.

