# **STUDY SYNOPSIS**

Protocol Title	SGLT2 Inhibitors in Cardiac Amyloidosis					
Protocol Number	3					
Design	This is a single center, single arm, prospective, 12 week open label pilot trial of the sodium-glucose cotransporter 2 inhibitor (SGLT2i), empagliflozin 10 mg oral daily, in patients with transthyretin amyloid cardiomyopathy (ATTR-CM), an age-related infiltrative cardiomyopathy that causes heart failure and death. The target population for enrollment will be subjects with ATTR-CM and either non-insulin dependent diabetes mellitus (DM) or chronic kidney disease (CKD). The primary aim will be to assess the safety and tolerability of empagliflozin 10 mg oral daily in subjects with heart failure secondary to ATTR, which remain unexplored. In addition, we will evaluate a number of secondary outcomes, including differences in daily diuretic dose, patient important outcomes using the Kansas City Cardiomyopathy Questionnaire (a validated health status measure for heart failure) and the Short Physical Performance Battery (a functional assessment), and potential mechanistic effects by evaluating changes in body composition, echocardiographic features, and cytokine and cardiorenal syndrome biomarker levels.					
	The accrual target is 15 subjects for this single arm pilot study assessing safety and tolerability of the study drug as the primary outcome.					
	Consented eligible patients will be evaluated for safety and tolerability of study drug, empagliflozin 10 mg oral daily, over a period of 3 months. During this time, subjects will undergo a total of 6 study visits: 3 in-person and 3 telephone follow-ups.					
Study Sites	This study is to be conducted at 3 locations at Columbia University Irving Medical Center: screening, recruitment, and in-person visits at the Center for Advanced Cardiac Care, Heart Center 4 th Floor; in-person visits, laboratory specimen collection, and echocardiography at the Clinical Cardiovascular Research Laboratory for the Elderly (CCRLE) at [name]; body composition analysis (including bioimpedance analysis and quantitative magnetic resonance) at the Body Composition Unit of NY Nutrition Obesity Research Center, located at [name].					

Time on Study	The duration of patient participation in this study is approximately 4 months.					
Primary Objective	To assess safety and tolerability of the SGLT2i empagliflozin in patients with ATTR-CM.					

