# The safety of study participants will be evaluated by:

- 1. Assessment of adverse events (AEs), including serious adverse events (SAEs).
- 2. Clinical laboratory safety tests (serum chemistry).
- 3. Vital sign measurements (blood pressure, pulse rate, and respiratory rate).
- 4. 12-Lead electrocardiogram (ECG).
- 5. Physical examinations
- 6. Scheduled phone follow-ups to screen for signs and symptoms related to study drug
- 7. Review of subjects' available medical records, including for urgent care or emergency room visits, hospitalizations, and office visits

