#### Power calculations:

Primary endpoint: A power calculation for our primary endpoint is not applicable in this pilot safety and tolerability trial.

Sample secondary (daily diuretic dose) endpoint power calculation: Based on prior literature, an estimated mean daily diuretic dose of 0.6 mg/kg with an effect size of 0.5 mg/kg, and a sample size of 15 total accrued subjects, will have 75% power to detect a difference in mean daily diuretic dose before and after study drug treatment using a two-sample t-test at the 5% level of significance.

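### As worded, the primary endpoint calls a serious adverse event rate above 30% acceptable, and it does not define the rate being measured

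*Combined protocol and SAP*

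**What the plan says.** The whole definition of the primary endpoint is one sentence in Statistical Procedures: "The primary endpoint for this pilot trial will be a serious adverse event rate greater than 30%, which is an acceptable rate". The 30% is said to be "based on prior clinical trial data with sodium-glucose cotransporter 2 inhibitors in subjects with heart failure over a 3 month period", but no rate, count or unit from those trials is given.

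The Study Synopsis sets the size: "The accrual target is 15 subjects for this single arm pilot study assessing safety and tolerability of the study drug as the primary outcome". Follow-up is 3 months (12 weeks).

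The only test that Statistical Procedures names is for other endpoints: "A matched-paired t-test will be used to test for a significant difference in the means of measured secondary endpoints". The Power calculations section adds one statement about the primary endpoint: "A power calculation for our primary endpoint is not applicable in this pilot safety and tolerability trial".

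The list of safety evaluations begins with adverse events, including serious ones, and does not limit them by cause. It gives no counting rule.

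**The concern.** This sentence holds the trial's only primary endpoint and its only safety benchmark. It has three gaps.

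- **Direction.** The relative clause attaches to a rate above 30%, so the sentence says that such a rate is acceptable. The aims and the synopsis speak of safety and tolerability but give no threshold that would correct this.
- **Definition.** The sentence gives an outcome (exceeding 30%) where it should name a variable. It does not say whether the numerator is subjects with at least one SAE or the number of SAEs. It does not say who is in the denominator, or how a subject lost before week 12 is counted.
- **Reporting.** A rate over 3 months is planned, but neither its formula nor an interval is given.

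The trial is open label with a single arm, so these choices could otherwise be made once the events are known. The section on future use of data says that the results may inform larger trials, so an ambiguous safety statement could carry forward.

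**Working it through.** **Inputs.** n = 15 (Study Synopsis); benchmark 30% (Statistical Procedures); period 12 weeks (Study Synopsis). The SAE rate in the prior trials is not given. The 30% has no calculation behind it and the primary endpoint has no stated power, so there is no figure of the plan's to reproduce.

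**1. Direction.** 0.30 × 15 = 4.5, so a rate above 30% means at least 5 of 15 if subjects are counted.

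| Subjects with an SAE | Rate | Literal wording | Likely intent |
|---|---|---|---|
| 4/15 | 26.7% | not in the range called acceptable | acceptable |
| 5/15 | 33.3% | acceptable | not acceptable |

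The observed rate is the same in both columns. Direction changes the verdict and leaves the number alone.

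**2. Counting unit.** Constructed example: 5 SAEs occur in 3 of 15 subjects.

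- Events per subject: 5/15 = 33.3%
- Subjects with at least one SAE: 3/15 = 20.0%

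Here the unit does move the number across 30%. Early losses can do the same. With 3 of 15 affected and 2 others lost, counting the losses as event-free gives 3/15 = 20.0%. Counting them as events gives (3 + 2)/15 = 33.3%.

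**3. Precision (supporting note).** The exact (Clopper-Pearson) two-sided 95% limits for x of n are:

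- lower = 2.5% quantile of Beta(x, n − x + 1), or 0 if x = 0
- upper = 97.5% quantile of Beta(x + 1, n − x)

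For n = 15:

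| x | Rate | 95% limits | Contains 30%? |
|---|---|---|---|
| 0 | 0% | 0% to 21.8% | no |
| 1 | 6.7% | 0.2% to 31.9% | yes |
| 4 | 26.7% | 7.8% to 55.1% | yes |
| 5 | 33.3% | 11.8% to 61.6% | yes |
| 8 | 53.3% | 26.6% to 78.7% | yes |
| 9 | 60.0% | 32.3% to 83.7% | no |

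So 30% lies inside the interval for every result from 1 to 8 of 15.

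**The case against.** The strongest reply is that this is a drafting slip in a small descriptive pilot. No one running a safety study would count more SAEs as success, and the natural reading of an SAE rate is the share of subjects with an SAE of any cause. Most of this stands as a statement of intent. It does not supply the missing text: the threshold appears in one sentence, that sentence points the wrong way, and nothing else in the available document corrects it.

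A reader might infer four stronger points that the documents do not support.

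- **That the sponsor means to treat a high SAE rate as a good result.** The stated aim is safety and tolerability, which argues against it. The defect is in the wording.
- **That only drug-related SAEs count.** One item in the list of safety evaluations is "Scheduled phone follow-ups to screen for signs and symptoms related to study drug". That describes what the calls look for. It does not limit the endpoint, and the first item in the list and the endpoint sentence carry no such limit.
- **That the trial is underpowered for its primary endpoint.** The plan claims no statistical separation from 30% and says openly that a power calculation does not apply. For a pilot that is acceptable. The width of the interval is a reason to report it, and a missing interval alone would be a lesser point.
- **That a formal decision rule is needed.** Such a rule would depend on the choice of interval: 1/15 excludes 30% by a one-sided 95% upper bound (27.9%) but not by the two-sided limit (31.9%). A rule on two-sided limits would also rarely decide. At an assumed true rate of 30% it gives no verdict with probability 1 − P(X = 0) − P(X ≥ 9) = 1 − 0.0047 − 0.0152 = 0.980.

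**Conclusion.** The concern holds for direction and definition. As written, the only primary endpoint labels rates above 30% acceptable, and it does not say how the rate is formed. Direction reverses the reading of a result such as 5/15. The counting unit can put the same data at 33.3% or 20.0%. The sentence must be corrected because it carries the trial's main conclusion.

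This rests on the available text, from which some front pages were removed. The examples of events and losses are constructed, and the 30% itself cannot be checked because the prior rates are not given. That 30% is meant as the highest acceptable rate is an inference for the sponsor to confirm.

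**What to change.** The sponsor should first confirm two things: that 30% is the highest acceptable rate, and that the 30% from prior trials is a proportion of subjects. If it is not, the benchmark must be restated on the scale of the endpoint. The sentence can then be replaced with:

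> The primary endpoint is the proportion of subjects with at least one SAE of any cause from first dose to the week 12 visit, among all subjects who took at least one dose of empagliflozin, reported with an exact (Clopper-Pearson) two-sided 95% CI and compared descriptively with a benchmark of 30%, the highest acceptable rate.

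The report should also give the total number of SAEs and the number of subjects lost before week 12 without a known SAE. It should not claim that the true rate is below or above 30% when the interval contains 30%.

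**Cost.** Only the wording of the statistical section changes. Adverse event review is already scheduled at baseline and at every contact to week 12. The planned review of "available medical records, including for urgent care or emergency room visits, hospitalizations, and office visits" can help find SAEs in subjects who miss visits. No extra subjects, visits, data items, power calculation or formal verdict rule are needed. The downside is that the safety conclusion becomes visibly less certain, since any result from 1 to 8 of 15 leaves 30% inside the interval.

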Sample Size	15 subjects					
Inclusion and Exclusion Criteria	Every participant must meet all of the following inclusion criteria to be eligible for enrollment in ALL parts of this study:					
	1. Age ≥ 18 years old					
	2. Diagnosis of TTR cardiac amyloidosis (wild type or variant), confirmed by the presence of amyloid deposits on analysis of biopsy specimens obtained from cardiac and noncardiac sites (e.g. fat aspirate, gastrointestinal sites, salivary glands, or bone marrow), technetium-99m pyrophosphate cardiac scintigraphy, or mass spectrometry					
	3. Normal serum free light chain ratio and the absence of abnormal monoclonal band on serum and urine immunofixation					
	4. Subjects will have at least 1 of the FDA-approved indications below for an SGLT2i, and meet package-insert criteria for drug initiation					
	a. Non-insulin dependent diabetes mellitus with hemoglobin A1c ranging from 6.5-9.9					
	OR					
	b. Chronic kidney disease (defined as an estimated glomerular filtration rate of 20-75 ml/minute/1.73 m  of body-surface area)					
	5. On stable oral diuretics (defined as no more than a 50% increase from baseline diuretic dose established during a sustained 2 week period) within 2 weeks before enrollment					
	6. Able to understand and sign the informed consent document after the nature of the study has been fully explained					
	The presence of any of the following excludes eligibility for enrollment in this study:					
	1. Prior liver or heart transplantation					
	2. Active malignancy or non-amyloid disease with expected survival of less than 1 year					
	3. Heart failure, in the opinion of the investigator, primarily caused by severe left-sided valve disease. Note : if valve was repaired, subject may be considered as no longer with severe valve disease					
	4. Heart failure, in the opinion of the investigator, primarily caused by ischemic heart disease					
	5. Current or anticipated ventricular assist device within the next 6 months					
	6. Pacemaker or implantable cardioverter defibrillator incompatible with magnetic resonance technology*					
	7. Absolute contraindication for quantitative magnetic resonance (e.g. aneurysmal clips, metal objects)*					
	8. Impairment from stroke, injury or other medical disorder that precludes participation in the study					
	9. Myocardial infarction, cardiovascular surgery, stroke or transient					

ischemic attack within the prior 90 days

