#### Aims

The specific aims of this investigation include:

- 1. To evaluate the safety and tolerability of SGLT2i therapy in patients with ATTR-CM and DM or CKD on oral loop diuretic therapy
- 2. To evaluate the change in oral loop diuretic daily dose in patients with ATTR-CM and DM or CKD on an SGLT2i.

- 3. To evaluate the effect of SGLT2i therapy on body composition in patients with ATTR-CM and DM or CKD.
- 4. To evaluate the effect of SGLT2i therapy on echocardiographic features of volume status in patients with ATTR-CM and DM or CKD.

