#### SCHEDULE OF ACTIVITIES

The following table summarizes the activities to be performed at each of the designated study visits. Details of the different procedures can be found in subsequent section of this protocol. For every study visit, a checklist will be used to help ensure completion of all the study procedures.

Procedure	Screening (within 30 days of baseline visit)	Baseline (day 1)	Week 1 (7 ± 2 days)	Week 4 (28± 3 days)	Week 6 (42± 4 days)	Week 8 (56± 5 days)	Week 12 (84± 7 days)
Site	Clinic	Clinic	Phone	Phone	Clinic	Phone	Clinic
Informed Consent	X						
Inclusion and Exclusion Criteria	X						
Baseline History		X					
Vitals Signs, Clinical Exam		X			X		X
Medications		X	X	X	X	X	X
Adverse Events Review		X	X	X	X	X	X
Electrocardiogram		X			X		X
Laboratory Analysis ‡		X	$X^{f}$		X		X
Transthoracic Echocardiogram		X					X
KCCQ		X			X		X
SPPB		X			X		X
Body Composition Analysis*		X			X		X

<sup>‡ Includes: NT-proBNP, troponin-t, basic metabolic panel, hepatic function panel, complete blood count, hemoglobin A1c (at baseline and week 12), uric acid, cystatin C, beta-hydroxybutyrate, erythrocyte sedimentation rate, c-reactive protein; urinalysis, urine albumin, urine uric acid, urine creatinine.

\*Body composition analysis includes bioimpedance and quantitative magnetic resonance measurements. As described in Inclusions and Exclusion Criteria section, a subset of study subjects may not be eligible for, OR may opt out of body composition analysis.

Laboratory analysis includes a single test, basic metabolic panel, to be drawn 7-10 days after study drug initiation to assess for significant flucations in renal function and ensure subjects' safety. Lab draw may be performed at CUIMC or locally to reduce subject burden.

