#### IV. Future use of data and/or specimens

Biobanked blood and urine specimens may be analyzed in the future for cytokine expression profiles, biomarkers of cardiorenal syndrome, and proteomics. Data collected during this pilot trial may be used for design and development of future larger trials of SGLT2i in subjects with ATTR-CM.

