#### VII. Non-invasive physical measurements\*

- a. At each of 3 in-person visits, subjects will first arrive to the Body Composition Unit of NY Nutrition Obesity Research Center, located at [name], where they will undergo body composition analysis. Subjects will be asked to change into a hospital gown, void, and undergo body weight measurement on a certified scale, and height measurement.
- b. Body composition analysis will be performed using 2 techniques: bioimpedance analysis (BIA) and quantitative magnetic resonance (QMR). Subjects with a pacemaker or implantable cardioverter defibrillator device will require an additional 20 minutes for interrogation and adjustment of their device settings before and after BIA and QMR scan to ensure no cardiac device interference and normal device functioning, a procedure which is consistent with standard of care for patients with cardiac electrophysiologic devices. Device adjustment and interrogation will be performed by [name], fellow in cardiovascular disease, under the supervision of [name], electrophysiology cardiology attending.

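### Does the diuretic-dose endpoint need a stated pre-treatment dose and body weight before it can be analysed?

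*Combined protocol and SAP*

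**What the plan says.** The Statistical Procedures section names among the secondary endpoints "mean change in daily diuretic dose (mg/kg of furosemide equivalence), mean change in body weight (kg) and total water content (kg"), and applies a paired t-test for a "significant difference in the means of measured secondary endpoints pre- and post-treatment" with three months of empagliflozin. The same section lists daily diuretic dose among the baseline characteristics to be summarised.

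Inclusion criterion 5 in the Study Synopsis requires stable oral diuretics in the two weeks before enrolment, with stability "defined as no more than a 50% increase from baseline diuretic dose established during a sustained 2 week period". It sets no limit on decreases.

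The Schedule of Activities has a column headed "Screening (within 30 days of baseline visit"), where eligibility is checked. Medications are not ticked there; they are ticked at Baseline (day 1) and at every later contact to week 12. Under Non-invasive physical measurements, subjects at each of the three in-person visits "undergo body weight measurement on a certified scale, and height measurement".

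The second aim is "To evaluate the change in oral loop diuretic daily dose in patients with ATTR-CM and DM or CKD on an SGLT2i". The design is a "single center, single arm, prospective, 12 week open label pilot trial" with 15 subjects, and safety and tolerability are the primary aim.

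**The concern.** A pre/post endpoint needs a defined pre value, and the documents attach the word baseline to two doses: the sustained dose of criterion 5 and the dose recorded at the day-1 visit. The entry rule allows them to differ. A subject who enters on a temporary increase and later returns to the sustained dose shows a fall measured from day 1 and no change measured from the sustained dose. With no control arm, nothing in the trial separates that fall from an effect of empagliflozin.

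This endpoint answers Aim 2 and is the only one with a power statement. The document also says that "Data collected during this pilot trial may be used for design and development of future larger trials of SGLT2i", so a spurious diuretic-sparing signal could be carried forward. The unnamed body weight adds a smaller question: weight is itself an endpoint, and dividing an unchanged dose by a lower week-12 weight makes the dose look higher.

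**Working it through.** **Which reading do the documents support?** Three places point the same way.
- The Medications row of the schedule starts at Baseline (day 1).
- Daily diuretic dose is summarised as a baseline characteristic beside KCCQ, SPPB and echocardiography, all first scheduled on day 1.
- The test compares values before and after three months of drug, and the last visit is week 12.

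The sustained two-week dose appears only inside an eligibility definition and is not a scheduled measurement. Day 1 to week 12 is therefore the natural comparison.

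**Inputs.** From Power calculations: mean dose 0.6 mg/kg, effect 0.5 mg/kg, n = 15, power 75%, 5% level. No SD is given, so the 75% cannot be reproduced directly; I solved for the SD that yields it (two-sided).
- Paired t-test, n = 15: standardised effect 0.731, so SD of differences = 0.5/0.731 = 0.684 and SE = 0.684/√15 = 0.177.
- Two-sample t-test, 15 values per time point: standardised effect 0.9965, so SD per time point = 0.5/0.9965 = 0.502. SD of differences = 0.502 × √(2(1 − r)). An assumed correlation r = 0.5 gives 0.502; r = 0.8 gives 0.317.

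**Gap for one subject who is 50% up.**
- Day-1 dose 0.6: sustained dose 0.6/1.5 = 0.4, gap 0.2, which is 0.2/0.5 = 40% of the planned effect.
- Sustained dose 0.6: day-1 dose 0.6 × 1.5 = 0.9, gap 0.3, which is 60% of the planned effect.

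These are illustrations. Decreases are not limited, and the dose may also move between enrolment and day 1.

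**Effect on the group mean and the test.** Assume no drug effect, a day-1 dose of 0.6, and k of 15 subjects who enter 50% up and revert fully. The mean shift is 0.2 × k/15. The rejection rate of the 5% paired test comes from the noncentral t with 14 df and noncentrality shift/(SD/√15), taking SD as the total SD of differences.

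| k (assumed) | Mean shift, mg/kg | Share of 0.5 | SD 0.684 | SD 0.502 | SD 0.317 |
|---|---|---|---|---|---|
| 3 | 0.040 | 8% | 5.5% | 6.0% | 7.4% |
| 5 | 0.067 | 13% | 6.4% | 7.7% | 11.8% |
| 8 | 0.107 | 21% | 8.7% | 12.0% | 22.8% |

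**Weight.** For an unchanged 0.6 mg/kg and an assumed loss of 1% or 5%:
- 0.6 × (1/0.99 − 1) = 0.006, or 1.2% of the planned effect.
- 0.6 × (1/0.95 − 1) = 0.032, or 6.3% of the planned effect.

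Against the paired SE of 0.177 these are 0.03 and 0.18 SE. The artefact runs against a diuretic-sparing finding.

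**The case for a change.** The strongest case for acting is that the gap in the text is real, closing it would be cheap, and the consequence may be larger than the table suggests. Many oral doses may not change at all over 12 weeks. If 11 subjects stay exactly where they were and 4 fall by the same amount, t = √(14 × 4/11) = 2.26 and p = 0.041, however small the falls. The sustained dose must be known to apply criterion 5, so recording it and repeating the comparison against it would need no extra visit.

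Part of this stands. The section does not name the visits or the weight, and one sentence would do so. The rest does not lead to a change:
- Naming day 1 leaves the reversal problem where it was, because the problem arises on the day-1 reading.
- Four falls of 0.2 mg/kg with eleven zeros have an SD of differences of 0.092. The plan's own power figure implies roughly 0.32 to 0.68 under the assumptions above, and at those SDs four reversals give rejection rates of 5.9% to 9.3%.
- A second comparison against the sustained dose is an optional extra for one secondary endpoint. Used as a condition for calling a fall a possible drug effect, it could hide a real one: if need had risen before entry and the drug allowed a return to the earlier dose, that comparison would show nothing.

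**Conclusion.** No change is needed. The missing visit labels and weight basis are details that an analyst would fill from the schedule: day-1 dose, week-12 dose, and a weight whose choice moves the result by about 0.006 to 0.032 mg/kg for a 1% to 5% loss. The possible bias from reversed increases belongs to the single-arm design, which the synopsis states openly, and it calls for cautious interpretation of any fall in dose.

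Its size is modest when few subjects are affected: 0.04 mg/kg, with rejection rates of 5.5% to 7.4%, at k = 3. It becomes material only if many enter on a temporary increase: 8.7% to 22.8% at k = 8. The documents do not say how often such increases occur or whether they reverse. Every figure also rests on full reversal from 50% up, no drug effect, and an SD solved back from the stated power. For one secondary endpoint of a 15-subject safety pilot, that does not justify amending the plan.
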